1.0 BACKGROUND AND HYPOTHESES

Cystic fibrosis (CF) is a genetic disorder characterized by a chronic cycle of airway infection, obstruction, and inflammation leading to progressive loss of lung function and eventual respiratory failure. Over the past decade the prevalence of infections involving *Methicillin Resistant Staphyococcus Auerus* (MRSA) in CF has increased dramatically.[1] Importantly, recent epidemiological studies have demonstrated that the presence of MRSA in the airways of patients with CF is associated with more rapid lung function decline [2] and a higher mortality [3]. Management of these patients includes prompt initiation of antibiotics at the onset of acute pulmonary exacerbations. A significant barrier to effective treatment is the limited number of safe and effective antibiotics for treatment of MRSA pulmonary infections. While vancomycin has been the mainstay of treatment for many years, its efficacy is limited by reduced susceptibility. In addition, the risk for acute kidney injury is significant in patients with CF due to the concomitant use of tobramycin for treatment of coinfection with *Pseudomonas aeruginosa*. While linezolid has demonstrated to be efficacious in the treatment of acute pulmonary exacerbations in CF, its use is significantly limited due to the high prevalence of depression (29-46%), which is often treated with selective serotonin reuptake inhibitors/serotonin non-epinephrine reuptake inhibitors(SSRIs/SNRIs) [4]. Tedizolid offers a significant advancement in the management of infections involving MRSA in CF due to its excellent activity, penetration into pulmonary secretions, proven safety, and reduced potential for drug interactions with antidepressants.

The pharmacokinetics of a number of medications has shown to be altered in patients with CF. [5,6] In general, patients with CF demonstrate an increased volume of distribution when expressed in liter/kilogram (L/Kg) of body weight, and increased renal clearance. In addition, the oral bioavailability of lipophilic medications is reduced due to pancreatic insufficiency. To our knowledge no study has evaluated the pharmacokinetics of tedizolid in patients with CF. The proposed study is designed to characterize the pharmacokinetics of intravenous and oral tedizolid in patients with CF and determine the optimal dosing regimen in preparation for future efficacy and safety studies in CF patients experiencing acute pulmonary exacerbations.

RATIONALE FOR SPUTUM TEDIZOLID CONCENTRATIONS:

Determination of the pulmonary penetration of antibiotics is vital to predicting the optimal dosing regimen for treatment of lung infections. Several different sampling methods are reported in the literature including bronchoalveolar lavage and induced or expectorated sputum. The choice of sampling technique is dependent upon multiple factors such as the site of infection, convenience, and need for serial samples. Cystic fibrosis is characterized by chronic respiratory infection/inflammation that leads to airway remodeling and progressive loss of lung function. The site of the infection/inflammation is predominately endobronchial rather than alveolar. This is consistent with the location of Cystic Fibrosis Transmembrane conductance regulator (CFTR) within the submucosal glands and acinar serous cells of the airways. Therefore, the ideal sample for drug concentrations would be from the endobronchial space which is best obtained by induced or expectorated sputum. Fiberoptic bronchoscopy, being invasive and costly, is poorly suited for serial sampling of airway secretions. In addition, bronchoscopy with lavage is thought primarily to sample the alveolar space rather than the airways alone. Numerous publications including those from our group have utilized expectorated sputum to successfully characterize the disposition of various antibiotics within the airways and determine optimal dosing regimens for treatment of airway infections in CF.²³⁻²⁸

Our study hypothesis is that tedizolid will exhibit excellent oral bioavailability and sputum penetration in patients with cystic fibrosis.

2.0 OBJECTIVES AND PURPOSE

Primary Objective:

Determine the steady-state concentrations of tedizolid in plasma and sputum of patients with CF.

Secondary Objective:

Determine the target attainment for the pharmacodynamic endpoint.

3.0 STUDY DESIGN

This study will be conducted using a prospective multiple dose, crossover design to characterize the steady-state pharmacokinetics of tedizolid intravenous/oral (IV/PO) in CF. A total of 12 adult patients with CF will participate in the study and will receive tedizolid 200mg IV or PO once daily for 3 doses followed by a minimum 2 day washout and receipt of the remaining dosage form.

4.0 DRUG/DEVICE INFORMATION

4.1 Tedizolid (Sivextro)

Tedizolid is an oxazolidinone antibiotic with potent activity against methicillin resistant *S. aureus* (MRSA). Tedizolid is approved for the treatment of acute bacterial skin and skin structure infections (ABSSSI) caused by designated susceptible bacteria.

The recommended dosage of tedizolid is 200 mg administered once daily orally (tablet) or as an intravenous infusion (IV) over 1 hour for six days.

The most common adverse reactions (incidence of > 2%) are nausea, headache, diarrhea, vomiting, and dizziness.

5.0 SELECTION AND WITHDRAWAL OF SUBJECTS

5.1 Inclusion Criteria:

CF patients admitted to the hospital for pulmonary exacerbation as defined by CF Pulmonary Guidelines and Fuchs et al (1994) (e.g. increased cough/sputum production, shortness of breath, chest pain, loss of appetite/weight, and lung function decline)

Diagnosis of CF based on positive sweat chloride or known CF mutation

Age > 18 years

Patients able to spontaneously expectorate sputum

CF patients with or without MRSA positive sputum will be included

5.2 Exclusion Criteria

AST/ALT > 3 x ULN

Thrombocytopenia (Platelets < 150,000)

Anemia (hematocrit < 30)
Any clinically significant abnormality noted on physical exam thought to interfere with the conduct of the study.
Pregnancy
No alcohol, nicotine, or caffeine-containing products during the study period
Patients taking monoamine oxidase inhibitors and/or serotonergic agents.

5.3 Withdrawal Criteria

Subject can be discontinued from the study for any of the following reasons:
Subject's personal reasons
Allergic reaction to the medication
Other significant study related adverse events

6.0 STRATIFICATION/DESCRIPTIVE FACTORS/RANDOMIZATION SCHEME

6.1 Stratification factors: Not applicable.

6.2 Descriptive factors: Not applicable.

6.3 Randomization:

Randomization sequence will be created using Excel 2007 (Microsoft, Redmond, WA, USA) with a 1:1 allocation using random block sizes of 2.

Subjects will be randomized to receive one of the two treatment sequences:

Oral Tedizolid for days 1 to 3 then Intravenous Tedizolid for days 10 to 12.

Intravenous Tedizolid for days 1 to 3 then Oral Tedizolid for days 10 to 12.

7.0 STUDY AGENT ADMINISTRATION OR INTERVENTION AND TOXICITY MANAGEMENT PLAN

7.1 Depending on the treatment arm of the study, you will receive Tedizolid administered in doses of 200 mg intravenously over 1 hour or 200 mg PO once daily for 3 doses.

AGENT	DOSE	ROUTE	DAYS	ReRx	NOTES
Tedizolid	200 mg	I.V. over 1 hours	1-3 or 10-12	Once daily	Total of 3 doses of IV and
Tedizolid	200 mg	PO	1-3 or 10-12	Once daily	Total of 3 doses of PO and

7.2 Criteria for removal from the study

7.21 A patient may always be removed from study whenever he/she wishes.

7.22 A patient may be removed from the study if they experience an allergic reaction to the medication.

7.3 Ancillary treatments.

Patients may continue to take their medications for treatment of CF

8.0 ASSESSMENT OF EFFICACY AND SAFETY

8.1 Side effects/Toxicities to be monitored.

Possible side effects of Tedizolid are:

The most common adverse reactions in patients treated with tedizolid were nausea (8%), headache (6%), diarrhea (4%), vomiting (3%), and dizziness (2%). The median time of onset of adverse reactions was 5 days for both Tedizolid with 12% occurring on the second day of treatment in both treatment groups.

Serious adverse reactions occurred in 12/662 (1.8%) of patients treated with Tedizolid and in 13/662 (2.0%) of patients treated with the comparator. Tedizolid was discontinued due to an adverse reaction in 3/662 (0.5%) of patients and the comparator was discontinued due to an adverse reaction in 6/662 (0.9%) of patients

The following selected adverse reactions were reported in Tediazolid treated patients at a rate of less than 2% in these clinical trials:

Blood and Lymphatic System Disorders: anemia

Cardiovascular: palpitations, tachycardia

Eye Disorders: asthenopia, vision blurred, visual impairment, vitreous floaters

General Disorders and Administration Site Conditions: infusion-related reactions

Immune System Disorders: drug hypersensitivity

Infections and Infestations: Clostridium difficile colitis, oral candidiasis, vulvovaginal mycotic infection

Investigations: hepatic transaminases increased, white blood cell count decreased

Nervous System Disorders: hypoesthesia, paresthesia, VIIth nerve paralysis

Psychiatric Disorders: insomnia

Skin and Subcutaneous Tissue Disorders: pruritus, urticaria, dermatitis

Vascular Disorders: flushing, hypertension

8.11 Patients will be asked about the presence of nausea, vomiting, diarrhea, or headache.

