8.12 CBC and CMP will be monitored at baseline

8.2 Adverse Event Reporting:

8.21 Any significant adverse events that occurs during the course of the study will be documented and reported.

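### Symptom questioning omits dizziness and has no stated schedule, and the last planned contact falls before or level with the 5-day median onset that the plan cites

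*Combined protocol and SAP*

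**What the plan says.** **The reactions expected.** Section 4.1 states: "The most common adverse reactions (incidence of > 2%) are nausea, headache, diarrhea, vomiting, and dizziness". Section 8.1, under its heading on toxicities to be monitored, repeats the five with rates of 8%, 6%, 4%, 3% and 2%, dizziness being the last. On timing it adds: "The median time of onset of adverse reactions was 5 days".

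**What patients are asked.** Section 8.11: "Patients will be asked about the presence of nausea, vomiting, diarrhea, or headache". It gives no day, frequency or end date.

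**The general duty.** Section 8.21: "Any significant adverse events that occurs during the course of the study will be documented and reported". The plan does not define which events count as significant.

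**The calendar (Appendix II).** There are rows for vital signs, baseline safety labs, dosing, and blood and sputum sampling, but none for adverse events. The last column is Day 10-14, which is the 48-hour sample after the third dose of the second form. No later contact is described.

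**The report.** Section 10.0 undertakes to report outcome status, including toxicity, for all eligible patients.

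**Timing of the second form.** Section 3.0 requires at least two days of washout, and the calendar columns let the second form start anywhere from Day 6 to Day 10. Sections 6.3 and 7.1 and calendar notes C to F put it on Days 10 to 12.

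**The concern.** Apart from vital signs, the 8.11 questions are the only safety assessment planned after dosing starts, because blood count and metabolic panel are taken at baseline only. Two features could make the toxicity report less complete than section 10.0 promises.

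First, a mild symptom that is asked about is usually recorded, and one that is not asked about depends on the patient raising it. Mild nausea would be picked up by 8.11. Equally mild dizziness would reach the record only if volunteered and judged significant. The five reactions would then be tabulated side by side although they were not collected in the same way.

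Second, if scheduled contact stops at about the time a typical reaction begins, later reactions to the second form have no planned route into the data. Reactions to the first form may surface between visits, or while the second form is being taken, and no rule says which form an event is recorded against.

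**Working it through.** **1. The plan's own figures.** The proportions in section 8.1 reproduce: 12/662 = 1.81%, 13/662 = 1.96%, 3/662 = 0.45% and 6/662 = 0.91%, against the printed 1.8%, 2.0%, 0.5% and 0.9%. The 5-day median is cited without data and cannot be re-derived. The sample size of 12 rests on similarity to other studies (section 13.2), so there is no formula to check.

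**2. What omitting dizziness could cost.** Inputs: n = 12 (section 13.2) and the per-patient rates p in section 8.1. Expected cases = 12p, and the chance of at least one case = 1 − (1 − p)^12.

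| Reaction | p | Asked in 8.11? | Expected in 12 | Chance of at least one |
|---|---|---|---|---|
| Nausea | 0.08 | yes | 0.96 | 63.2% |
| Headache | 0.06 | yes | 0.72 | 52.4% |
| Diarrhea | 0.04 | yes | 0.48 | 38.7% |
| Vomiting | 0.03 | yes | 0.36 | 30.6% |
| Dizziness | 0.02 | no | 0.24 | 21.5% |

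For dizziness, 1 − 0.98^12 = 0.215. This assumes that the cited rates carry over to this population and to these short courses.

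**3. Time from first dose to last contact.** If the first dose of a form is on day d, the third is on day d + 2 and the 48-hour sample is on day d + 4. For the second form the calendar gives 10 − 6 = 4 days (earliest start) or 14 − 10 = 4 days (latest start). If the first dose is day 1, the last contact is on treatment day 5. Against a median of 5 days, the last contact is therefore one day early (elapsed days) or level (treatment-day count).

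**4. Share of reactions starting at or after the last contact, if the median carried over.**
- Treatment-day count: 50%, by definition of the median.
- Elapsed days, exponential onset with median 5: 0.5^(4/5) = 57%.
- Elapsed days, Weibull onset with median 5, treating the 12% that section 8.1 gives for the second day as cumulative to day 2: k = ln[−ln(0.88)/ln 2]/ln(2/5) = 1.845, so the share is 0.5^[(4/5)^1.845] = 63%.

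The range is 50% to 63%. The two curves are illustrations; the documents give no onset distribution.

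**5. Where late first-form reactions fall.** The first form starts on Day 1 and its scheduled contact ends on Day 5.
- Second form from Day 6 (Days 4 and 5 drug-free): a first-form reaction at 5 elapsed days falls on Day 6, when the second form begins.
- Second form from Day 10 (Days 4 to 9 drug-free): first-form reactions at 5 to 8 elapsed days fall on Days 6 to 9, with no visit scheduled and no second form being taken. Only those at 9 or more elapsed days overlap the second form.

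**The case against.** The strongest reply is that the plan never says when questioning stops. A reader might infer that it ends 4 days after the first dose of the second form, and that reactions will therefore be missed or credited to the wrong form. The documents do not support that. The 4 days is the timing of the last sampling visit, and the firmer finding is that no schedule is stated.

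The remaining objections also carry weight:

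- **Day counting.** Section 8.1 speaks of the second day of treatment, and the calendar starts at Day 1. On that count the last contact is level with the median and not before it. This stands, although about half of onsets would still lie at or after that point.
- **Relevance of the median.** The figure comes from earlier trials, and section 4.1 describes the recommended regimen as "administered once daily orally (tablet) or as an intravenous infusion (IV) over 1 hour for six days". Each form here is given for three doses. Nothing in the documents shows that the onset pattern transfers, so any share derived from it is conditional.
- **Attribution.** Overlap with the second form at the median onset arises only with the shortest washout. On Days 10 to 12 most late first-form reactions would fall in the gap, and patients could still report them at second-period contacts. The plan has no rule crediting events to a form and no safety comparison between forms.
- **The symptom list.** Section 8.11 is not called exclusive, and 8.21 remains as a safety net. That net covers significant events only, so the difference in ascertainment for mild dizziness remains.
- **Stakes.** Safety is neither a primary nor a secondary objective (section 2.0), the analysis is descriptive, and the chance of no dizziness case at all is 78%.

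**Conclusion.** The point holds as a minor, inexpensive improvement.

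Two parts need no assumption about onset: dizziness is left out of 8.11 although the plan twice names it as common, and the questions have no schedule. The expected loss from the first is small: 0.24 cases, with a 21.5% chance that at least one patient is affected, at the cited 2%.

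The timing part is conditional. The last scheduled contact is before or level with the cited median, depending on how days are counted. About half of second-form reactions (50% to 63% in the illustrations) would start at or after it only if the earlier-trial median applies to a 3-dose course. Wrong-form attribution is a possibility under the shortest washout and not an expected result. If reactions cluster around the three dosing days, both effects shrink.

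What is affected is the completeness of the toxicity description. No concentration, bioavailability or target-attainment result changes.

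**What to change.** 1. Add dizziness to the list in section 8.11.
2. Add an adverse-event row to the existing calendar days, recording onset date and the form last taken. Vital signs are already due in every column, so this adds no visit. It should also apply when the 24- and 48-hour samples are taken at home, since section 11.0 gives the outside phlebotomist no symptom questions.
3. Add one closing telephone contact several days after the last 48-hour sample, clearly beyond the cited median under either day count. A call placed just past the median would still precede nearly half of onsets on the same reasoning, so the margin matters. Telephone reminders are already used for oral doses (calendar notes D and E).
4. Reconcile the start of the second period: the two-day minimum washout and the Day 6-10 column against Days 10 to 12 in sections 6.3 and 7.1 and the calendar notes.

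The cost is one word, one calendar row, 12 telephone calls and slightly longer follow-up.

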8.12 CBC and CMP will be monitored at baseline

8.2 Adverse Event Reporting:

8.21 Any significant adverse events that occurs during the course of the study will be documented and reported.

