Appendix I: Informed Consent
Appendix II: Study Calendar

	Screening	Day 1	Day 2	Day 3	Day 4	Day 5	Day 6-10	Day 7-11	Day 8-12	Day 9-13	Day 10-14
Informed Consent	X										
Medical History	X										
Medication History	X										
Height, weight	X										
Vital signs ^A	X	X	X	X	X	X	X	X	X	X	X
Safety labs ^B	X										
IV drug administration ^Q		X ^C	X ^C	X ^C			X ^F	X ^F	X ^F		
PO drug administration		X ^E	X ^E	X ^E			X ^D	X ^D	X ^D		
Blood Pharmacokinetics (PK) ^G				X					X		
Sputum Pharmacokinetics (PK): pre dose ^H				X							
Sputum PK: 0.5 to 1 hour post dose				X ^I					X ^I		
SputumPK: 2 hours post dose				X ^J					X ^J		
SputumPK: 3 hours post dose				X ^K					X ^K		
SputumPK: 4 hours post dose				X ^L					X ^L		
SputumPK: 8 hours post dose				X ^M					X ^M		

SputumPK:Q 24 hours post dose					X ^O					X ^O	
SputumPK:Q 48 hours post dose						X ^P					X ^P

- A. Vital signs to include blood pressure, heart rate, temperature, respiratory rate.
- B. Safety labs to include complete blood count with differential, complete metabolic panel
- C. For the treatment arm A: IV Tedizolid will be done on days 1 to 3.
- D. For the treatment arm A: PO Tedizolid will be done on days 10 to 12. Days 10 and 11 the dose of oral Tedizolid will be done at home for the subject. A telephone call will be done to remind the subject to take the PO Tedizolid.
- E. For the treatment arm B: PO Tedizolid will be done on days 1 to 3. Days 1 and 2 can be done at home. A telephone call will be done to remind the subject to take the PO Tedizolid.
- F. For the treatment arm B: IV Tedizolid will be done on days 10 to 12.
- G. All subjects will have a pre dose blood PK levels, 0.5 hour, 1, 2, 3, 4, 8, 24 and 48 hours post dose of Tedizolid (IV or PO). A 5mL EDTA tube will be used to collect the blood PK sample.
- H. All subjects will have a pre dose sputum sample (IV or PO).
- I. Subject number 1-3 will need to produce a sputum sample at this time period (IV or PO).
- J. Subject number 4-6 will need to produce a sputum sample at this time period (IV or PO).
- K. Subject number 7-9 will need to produce a sputum sample at this time period (IV or PO).
- L. Subject number 10-12 will need to produce a sputum sample at this time period (IV or PO).
- M. Subject number 1-4 will need to produce a sputum sample at this time period (IV or PO).
- N. Subject number 5-8 will need to produce a sputum sample at this time period (IV or PO).

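### Blood-count and liver-enzyme reactions are listed for monitoring, but CBC and CMP are scheduled only before dosing, so laboratory toxicity would be unassessed, not shown to be absent

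*Combined protocol and SAP*

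**What the plan says.** All references are to the combined protocol and SAP.

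- Section 8.1 is headed "Side effects/Toxicities to be monitored". Among the reactions it lists are "Blood and Lymphatic System Disorders: anemia" and "Investigations: hepatic transaminases increased, white blood cell count decreased", described as having been reported "at a rate of less than 2% in these clinical trials".
- Two numbered items under that heading say what will be done. Section 8.11: "Patients will be asked about the presence of nausea, vomiting, diarrhea, or headache". Section 8.12: "CBC and CMP will be monitored at baseline".
- Section 8.21: "Any significant adverse events that occurs during the course of the study will be documented and reported".
- Appendix II (Study Calendar) has a safety-labs row with one mark, under Screening. Footnote B defines the row: "Safety labs to include complete blood count with differential, complete metabolic panel".
- Section 10 undertakes to report outcome status, with toxicity named first, for all eligible patients.
- Section 11 and calendar footnote G schedule blood for tedizolid concentrations after the third dose of each dosage form, out to 48 hours.
- Section 12 says that laboratory data go on the case report form, without saying which tests or when.

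**The concern.** Low white cells and raised transaminases are laboratory findings by definition, and anemia is reliably shown only by a blood count. One sample taken before the first dose fixes the starting value but cannot show a change after treatment. The plan therefore names three reactions for monitoring, promises a toxicity report, and schedules no measurement that could supply its laboratory part.

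Two things are at stake. The first is how the results are read: if the report says that no hematologic or hepatic toxicity was seen, a reader may take this as evidence of safety when nobody looked. The second is the individual patient. Section 5.3 allows discontinuation for a significant study-related adverse event, but a laboratory change without symptoms cannot enter that decision unless someone outside the protocol happens to test for it. Section 8.3 says that a data monitoring committee is not applicable, so no such committee would pick it up either.

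**Working it through.** The plan gives no figure on this point to reproduce. The percentages in Section 8.1 that come with counts are arithmetically sound: 12/662 = 1.81%, 13/662 = 1.96%, 3/662 = 0.45% and 6/662 = 0.91%, against the stated 1.8%, 2.0%, 0.5% and 0.9%.

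**Step 1. What is listed against what is measured after dosing.**

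| Reaction listed in 8.1 | Test that would show it | Scheduled before dosing | Scheduled after dosing |
|---|---|---|---|
| Anemia | CBC | Yes (8.12, calendar) | No |
| Low white cells | CBC | Yes | No |
| Raised transaminases | CMP | Yes | No |

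The calendar has 11 columns: Screening, Days 1 to 5, and five more ending at Day 10-14. Safety labs are marked in 1 of 11, and in 0 of the 10 dosing and follow-up columns. Section 8.12 and the calendar agree, so this is not a damaged table.

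**Step 2. Other post-dose safety checks.** These are vital signs (calendar), four symptom questions (8.11) and reporting of significant adverse events (8.21). None of them measures a blood count or an enzyme. The post-dose blood samples are for drug assay only.

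**Step 3. Draws already planned.** From Section 11 and footnote G, blood is taken after dose 3 on the dosing day (0.5 to 8 h), at 24 h and at 48 h. That is 3 post-dose draw days per period, and 3 × 2 = 6 per patient. In the first period the 24 h and 48 h draws fall on Days 4 and 5. Both precede the second course whether it starts on Day 6-10 (calendar columns) or on Day 10 (Sections 6.3 and 7.1, footnotes D and F). The documents disagree on that start day, and the passages must be reconciled.

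**Step 4. What testing would yield.** Inputs: n = 12 (Section 3) and a true rate p for each reaction. The documents say only that the rate is below 2%, so p = 0.5%, 1% and 2% are my assumptions. I also assume that the sample catches every case. The chance of at least one case of a given reaction is 1 − (1 − p)^12:

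- p = 0.5%: 1 − 0.995^12 = 5.8%
- p = 1%: 1 − 0.99^12 = 11.4%
- p = 2%: 1 − 0.98^12 = 21.5%

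For at least one case of any of the three, with equal rates and independence (a further assumption), the exponent is 36, and the results are 16.5%, 30.4% and 51.7%. If no case of a given reaction were seen in 12 tested patients, the one-sided 95% upper bound on its rate would be 1 − 0.05^(1/12) = 22.1%. Under the current schedule, the chance of detection by a protocol-scheduled test is zero, because there is no such test.

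**The case against.** The strongest reply is that the list in 8.1 is background. It is introduced as possible side effects and as findings from earlier trials. The items that say what this study will do are 8.11 and 8.12, both numbered under the same heading. If the list committed the plan to a test for each entry, it would also need schedules for vitreous floaters and facial nerve paralysis. This has force: the passages do not flatly contradict each other, since 8.12 is itself part of 8.1. But the heading still presents the list as what is to be monitored, and 8.12 uses the word monitored for a single baseline sample. If the list is only background, the plan should say so.

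A reader might go further and infer that these reactions cannot be observed at all, or that the plan will report them as absent. The documents do not support either reading. Patients are in hospital at entry (Section 5.1), 8.21 covers any significant adverse event, and Section 12 collects laboratory data, so an abnormality found in routine care could be reported. Nothing says that unmeasured toxicity will be counted as absent. What stands is narrower: no passage schedules or requires a post-dose value, some oral doses may be taken at home (footnotes D and E), and Section 11 allows for early discharge. Detection would be haphazard.

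A reader might also infer that the platelet, hematocrit and AST/ALT limits in Section 5.2 ought to be rechecked before the second course. The plan uses them only as exclusion criteria and states no such rule, so leaving them unchecked contradicts nothing.

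Finally, Section 10 reads like carried-over text, since it also promises survival and time-to-failure results in a 12-patient pharmacokinetic crossover. That weakens it as a sign of intent, but the current text still commits the plan to reporting toxicity.

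**Conclusion.** The concern holds in this form: the plan lists three laboratory reactions for monitoring and promises to report toxicity, yet schedules no CBC or CMP after the first dose in any of 12 patients. The laboratory part of the toxicity outcome would be not assessed, apart from whatever routine care or symptoms happen to reveal.

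This rests on a direct reading of Sections 8.1, 8.12 and 10 and the calendar, and on no assumed rate. The assumed rates matter only for the value of testing, which is small for estimation: with none seen in 12, a rate as high as 22.1% could not be excluded. Both objectives in Section 2 are pharmacokinetic or pharmacodynamic, and exposure is three doses per route. No stated endpoint changes. The gain is in individual patient safety and in a report that does not present missing measurement as absence of harm. It should be corrected, but it does not threaten the study's main purpose.

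**What to change.** Reconcile Sections 8.1, 8.12 and 10 and the calendar by one of two routes. The choice is the sponsor's.

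1. **Measure.** Add a CBC/CMP tube to one post-dose pharmacokinetic draw already planned in each period, for example at 24 h or 48 h after dose 3. Mark it in the calendar's safety-labs row, amend 8.12, and state that changes from baseline will be summarized descriptively. The cost is 12 panels per added time point, so 12 × 2 = 24 for one draw in each period, with no extra venepuncture. Section 11 allows the 24 h and 48 h draws to be taken at home and moved by courier, so some added handling is needed there.
2. **State the limit.** Say in 8.1 that the list is background from earlier trials, and in 8.1 and Section 10 that laboratory toxicity is not systematically assessed and that no conclusion about it will be drawn. Replace the word monitored in 8.12 with wording that describes a baseline check. This costs only the edit.

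Under either route, Section 12 should say which laboratory data are recorded, when, and whether routine-care results are included.
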